9 CHANGES IN CONDUCT OR PLANNED ANALYSES FROM THE PROTOCOL

- Dynamic randomization will include all stratification variables, including WAZ in determining the treatment allocation.
- Populations for secondary endpoints previously PP, changed to Safety with results to be reported for PP populations as sensitivity analysis.

Confidential Page 21 of 50

10 OVERALL STATISTICAL CONSIDERATIONS

10.1 General Conventions

Descriptive statistics will be presented for continuous data with applicable decimal precision as follows in relation to the source data (indicated as N+x), with a maximum of 3 decimals to be displayed:

- Number (N).
- Mean, (N+1).
- Number of missing observations, (N).
- Standard deviation (SD), (N+1).
- Median, (N+1).
- Minimum, (N+1).
- Maximum, (N+1).

Absolute and relative frequencies will be used to describe categorical variables. Unless otherwise specified, the denominators for percentages will be the number of participants in each intervention group with non-missing data for the variable of interest at the summarized visit. Percentages will be presented with 1 decimal place and a percent sign (%).

All statistical testing will be 2-sided and performed at the 0.05 level. When reporting the results of significance tests p-values will be reported. All confidence intervals will be 2-sided at the 95% level, unless otherwise stated.

Study day is calculated relative to the first study intervention administration on Day 1.

Confidential Page 22 of 50

- If the current ACR date is after study intervention administration: Study Day = (Current ACR Date – Study Intervention administration Date) + 1
- If the current ACR date is before study intervention administration:

Study Day = (Current ACR Date – Study Intervention administration Date)

Study day will not be calculated if either the current ACR or the study intervention administration date is incomplete or missing.

The following periods for the study are defined:

- Treatment Period: Day 1 through last dose of participant.
- Follow-up Period: Day of last dose of participant + 1 up to EoS.

SAS® code of SAS® procedures that will be used to perform efficacy and safety analyses is provided in Appendix 3.

10.2 Baseline Definition

Baseline is defined as the last available value prior to the participant receiving the first dose of the study intervention. If the potential Baseline ACR is on Day 1 (and time is not recorded), it is assumed that the ACR occurred before the first dose of the study intervention was received.

CFB is calculated as:

$$CFB = Observed\ value - Baseline\ Value$$

10.3 Handling of Missing Data

10.3.1 Missing or Partial Dates for Adverse Events

Missing or partial AE start dates will be imputed for the purpose of determining whether the AEs are treatment emergent. Data handling rules for missing or partial start/stop date for AEs are detailed in Appendix 2Table 6. The missing or partial dates will be displayed in the data listings as reported on the eCRF rather than the imputed dates.

10.3.2 Missing or Incomplete Dates for Prior or Concomitant Medications

Missing or partial medication start or stop dates will be imputed for the purpose of determining whether the medication is taken concomitantly. Data handling rules for missing or partial start/stop date medications are detailed in Appendix 2 Table 7. The missing or partial dates will be displayed in the data listings as reported on the eCRF rather than the imputed dates.

10.3.3 Missing Efficacy data

Missing efficacy data will not be imputed.

Confidential Page 23 of 50

10.4 Interim Analysis

No interim analysis is planned.

10.5 Pooling Strategy for Study Sites

Data will be pooled by country: Bangladesh, Kenya, Pakistan, and Tanzania (the sites that are included in each geography should be identified clearly). Analysis of the primary endpoint will include country in the model as a covariate. A random effect for site may be included based on model comparisons with and without the effect.

10.6 Visit Windows/Unscheduled Visits

Data at each visit are to be captured within the following windows for each of the intended visits:

Table 4. Visit windows

Visit name	Visit window	
Screening	≤ 7 days before randomization	
Randomization	Day of hospital discharge, Day 1	
Clinic Visit 1	Day 1	
Home Visits at Week 1	Within ± 1 day of Day 7, ie, Days 6-8	
Home Visit at Week 2	Within ± 1 day of Day 14, ie, Days 13-15	
Home Visit at Week 3	Within ± 1 day of Day 21, ie, Days 20-22	
Clinic Visit 2	Within ± 1 day of Day 28, ie, Days 27-29	
Home Visit at Week 5	Within \pm 2 days of Day 35, ie, Days 33-37	
Home Visit at Week 6	Within \pm 2 days of Day 42, ie, Days 40-44	
Home Visit at Week 7	Within ± 2 days of Day 49, ie, Days 47-51	
Clinic Visit 3	Within ± 2 days of Day 56, ie, Days 54-58	
Clinic Visit 4	Within \pm 2 days of Day 90, ie, Days 88-92	

Additional visit windowing will not be applied. Unscheduled visits will not be included in by-visit summary tables or analysis but may contribute to the Baseline value and listed in by-participant data listings. In the case of a retest (same visit number assigned), the latest available test result as provided in the data transfer for that visit/time point will be used for by-visit summaries.

Confidential Page 24 of 50

11 STATISTICAL ANALYSIS METHODS

11.1 Participant Disposition

The following will be presented in a summary table by treatment and overall, for disposition:

- Number of participants screened.
- Number of screen failures.
- Reasons for screen failures.
- Number of participants re-screened.
- Number of participants randomized (ITT population).
- Number of participants randomized but not treated.
- Number of participants who received treatment (Safety population).
- Number of participants who completed the 28-day study intervention period.
- Number of participants who discontinued treatment with reasons.
- Number of participants who completed study up to Day 56 visit.
- Number of participants who withdrew from study prior to Day 56 visit with reasons.
- Number of participants who completed study (up to Day 90 visit).
- Number of participants who withdrew from the study between Days 56 and 90 visits with reasons.

The denominators for the number of participants who completed the 28-day study intervention period and discontinued treatment with reasons will be the obtained from the Safety population. A participant listing for disposition for all participants will be presented including treatment arm, country, study site, date of first and last dose, completed/discontinued treatment with reason and date, completed/withdrew from study with reason and date.

A table summarizing the populations for analysis (including the reasons for exclusion) will be presented by treatment group and overall. A listing will be presented for the ITT population with population excluded from and reasons for exclusion from analysis population for mITT and PP.

A participant listing with randomization information for the ITT population will be provided, including WAZ and age at enrollment (Study Day 1), country, discharge destination date and time of randomization and treatment group. For all participants who are screen failures the following information will be listed: informed consent date, reason for screen failure and eligibility criteria not met.

Important protocol deviations are a subset of protocol deviations that may significantly impact the completeness, accuracy and/or reliability of study data or that may significantly affect a participant's rights, safety or well-being. Important protocol deviations will be summarized in a table by treatment group and overall and all protocol deviations will be listed, including date of deviation, deviation category (important/unimportant), standard protocol deviation term and protocol deviation description.

Confidential Page 25 of 50

11.2 Demographics and Baseline Characteristics

Demographics and baseline characteristics will be summarized using descriptive statistics by treatment group and overall. The denominators for percentages will be the number of participants in each treatment group with non-missing data for the variable of interest for the ITT population. The number of participants with missing data at baseline, without percentages, will be displayed for each of the variables. Two participant listings will be presented with treatment group, one for demographic variables and the other for baseline variables as listed below, for the ITT population.

The following demographic and baseline variables will be summarized and listed:

- Country (Bangladesh, Kenya, Pakistan, Tanzania).
- Age (days) at enrollment both numeric and categorical (30-59 days, 60-120 days).
- Sex (Male, Female).
- Race (Asian, Black, Indian, White, Other).
- Ethnicity (Bantu, Bengali, Cushite, Kalenjin, Kikuyu, Luo, Luyha, Nilo-Hamite, Pashtun, Punjabi, Sairiki, San, Sindhi, Other).
- Infant been exposed to HIV (Human immunodeficiency virus) (Yes, No).
- Type of HIV exposure (Hospital, Household, Infected Mother, Other, Unknown).
- Infant HIV status, only positive will be indicated as it will be recorded in the medical history.
- Weight (grams).
- Length (cm).
- Mid-upper arm circumference (MUAC).
- Head circumference (cm).
- Skinfold thickness at the subscapular and triceps (mm).
- Bilateral pedal edema (Yes, No).
- Weight-for-age z-score (WAZ) both numeric and categorical (-3 to -2, \leq -3).
- Weight-for-length z-score (WLZ).
- Birth weight (grams).
- Gestational age (weeks).
- Birth delivery method (C-Section, Vaginal birth).
- Discharge destination (Home, Nutritional Rehabilitation Unit).
- Primary type of feeding the infant has received since birth (Exclusively breastmilk, Formula exclusively, A mix of breastmilk and other types of feedings, Other milk exclusively).
- Antibiotics received within prior 30 days (Yes, No).
- Have refrigerator in house (Yes, No).

Confidential Page 26 of 50

See Section 11.5.1 for the calculation of WAZ, Section 11.6.6 for the calculation of WLZ and the derivations of baseline values of MUAC and head circumference.

11.2.1 Vaccinations

The number and percentage of participants who received vaccinations up to the time of screening will be presented by treatment and overall, in a table for each vaccination recorded. Concomitant vaccinations will be summarized similarly in a separate table. A participant listing including the date and name of vaccination will be provided. The tables and listing will be presented for the ITT population.

11.2.2 Socioeconomic status Estimation

An estimation of SES will be captured using a survey to assess household wealth which is publicly available from CHAIN and based on the DHS 7 questionnaire [1].

Maternal education and type of water use will be presented in a summary table using frequencies and proportions for the ITT population. The categories are given by:

- Highest level of maternal education (None, Primary, Secondary, Above Secondary, Unknown, Other, N/A care home).
- Type of water use (Treated water, Untreated water).

Type of water use is derived from "Do you usually do anything to the water to make it safer to drink?" as follows:

- Treated water: Bleach/chlorine, strain through a cloth, let it stand and settle, Use water filter, solar disinfection, boil, Other.
- Untreated water: None.

Highest level of maternal education, if anything is done to water to make it safer to drink and type of water use will be presented in a participant listing.

11.2.3 Medical History

A full medical history will be recorded at screening to assess enrollment eligibility and to provide a baseline. All conditions that exist before and during screening will be recorded in the medical history.

Medical history terms will be coded using the latest version of the MedDRA.

Medical history, including prior procedures, will be summarized by treatment group and overall, in a table by SOC and, PT for the Safety population. The number and percentage of participants who had at least 1 condition will be shown. Participants with multiple medical histories within a SOC or PT are counted only once for that SOC and PT. A participant listing for the ITT population will be presented.

Confidential Page 27 of 50

No imputation of partial or missing dates will be performed for medical history and study days will not be presented for these cases.

11.3 Prior and Concomitant Medications and Procedures

A prior medication is defined as having started and ended prior to first dose of study intervention. A concomitant medication is defined as either having started prior to first dose of study intervention and ended on/after first dose of study intervention, is ongoing at Baseline or, having started on/after first dose of study intervention. Medications will be coded by site of action and therapeutic and clinical characteristics using WHO's ATC Classification.

The number and percentage of participants reporting prior and concomitant medications will be summarized separately by ATC Class and preferred name, by treatment group and overall.

The same table will be presented for concomitant medications for the mothers of the participants.

The following ATC class/terms for probiotics and antibiotics will be used to identify the participants for the subgroup analysis based on infant concomitant antibiotic/probiotic use (see Section 8.2):

- A07FA01 Lactic acid producing organisms (probiotics).
- A07FA02 Saccharomyces boulardii (probiotics).
- A07FA51 Lactic acid producing organisms, combinations (probiotics).
- J01 (antibiotics).
- J04 (antibiotics).

Prior/concomitant status (according to the definition provided at the start of this section) will be derived using the medication start and stop dates. For partial dates, see imputation rules in Appendix 2.

Reason for use, dates of administration including start and end dates, dosage information including dose and frequency of any medication or vaccine (including over-the-counter or prescription medicines, vitamins, and/or herbal supplements) that the participant was receiving at the time of screening or received during the study will be presented in participant listings for infants and mothers.

All procedures will be classified according to the latest version of MedDRA. The number and percentage of participants reporting concomitant procedures will be summarized separately by SOC and PT, by treatment. Concomitant procedures are defined as having been performed on or after the date of the first dose of study intervention. Procedures will be presented in a participant listing. The listing will include the start and stop dates of the procedures, whether it is related to an AE, reason for procedure, interpretation of procedure and findings.

The Safety population will be used to present prior and concomitant medication and procedures tables. The ITT population will be used for listings.

Confidential Page 28 of 50

11.4 Study Intervention Compliance and Exposure

Participant compliance with study intervention will be assessed at each visit. Compliance will be assessed by counting returned doses, and by asking the mother if her infant received a dose each day, and if any of the additional doses were administered and why. Deviations from the planned dosing regimen will be recorded in the eCRF.

The compliance is defined as

$$CS = 100 \times \frac{Number\ of\ doses\ administered}{Number\ of\ days\ on\ study\ intervention}\%$$

where

- Number of doses administered: is the actual number of doses administered as per exposure eCRF. If a dose was re-administered due to vomiting within 30 minutes/spitting out the dose will be counted as one dose. Deviations from planned dosing regimen will be used to consider if doses were used but not administered for any reason. According to the CRF completion guidelines, doses that were spilled without any part administered, were recorded as zero doses used. If a second dose was used and administered on the same day, it was recorded in a second record in the database.
- Number of days on study intervention: calculated as the number of days during the treatment period which participant could have received treatment. Days on which treatment/study was discontinued does not form part of denominator.

Descriptive statistics of the compliance will be summarized in a table by treatment group and visit (Day 7, 14, 21, 28, Combined Day 1 to 28). For weekly summaries, compliance is calculated based on the period between the preceding visit and the current. The frequency and percentage of participants who achieved 100% compliance score over the entire treatment period will be presented by treatment group in the same table.

The number of doses administered will be presented in a separate table using descriptive statistics (mean, SD, median, min, max) by treatment group and visit. Additionally, the number and percentage of participants will be presented in the same table according to the following intervals for doses administered:

- 28 doses (100% of doses taken)
- 14 to 28
- < 14

The proportion of infants who had x% of doses for each of the dose administer and reconstitution scenarios (see Section 11.4.2), including partial doses, doses mixed in breastmilk, doses mixed in water and doses vomited within 30 minutes of administration, will be summarized using summary statistics in a table by treatment according to the following categories:

- 100%
- 75% to 99%

Confidential Page 29 of 50

- 50% to 74%
- 25% to 49%
- < 25%

A histogram of compliance scores will be presented by treatment group for the compliance scores across the treatment period (Day 1 to 28). An additional histogram by treatment group will be presented for number of doses administered.

The exposure listing will include date of study intervention administration, whether the dose is the first dose or the last, deviations from planned dosing regimen, reason for non-compliance, what study powder was mixed in, vomiting after intake of study intervention and whether or not a second dose was administered following vomiting.

Another listing will be provided with compliance scores across weekly intervals during the treatment period, as well as over the entire treatment period. It includes the start date of the interval for which compliance is calculated, number of days on treatment in interval, number of doses of study intervention used, number of doses vomited within 30 minutes, number of doses administered and the calculated compliance.

The Safety population will be used for the table summaries. The summary of study intervention compliance table will also be presented for the mITT population. Listings will be presented for the mITT population.

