6.4. Feeding History

The mother of the participating infant will be asked to complete a diary to record the number and types of feedings (e.g., breast-feeding, formula feeding, other) daily through Day 90.

The type of liquid (breastmilk or water) used to mix with the Bi-26 or placebo, whether the full dose was taken, and whether a repeat dose was administered will also be recorded in the diary for Days 1 through 28.

The completed diary should be collected by the site staff.

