8.1.5 Per-Protocol (PP) Population

All participants randomly assigned to study intervention, who received the study intervention, have a Day 90 visit, and did not substantially deviate from the protocol procedures. Important protocol deviations will be evaluated individually by the sponsor to decide whether it has basis to exclude a participant from the PP population. Deviation from study intervention compliance (see Section 11.4) is defined as compliance of less than 80%. Participants will be analyzed according to the intervention they actually received (for details refer to Section 11.1).

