8.2 Subgroups

To assess consistency of effects, subgroup analyses may be performed in selected subgroups such as:

- WAZ strata: < -3 and between -3 and -2 (boundaries excluded).
- Age: 30 to 59 days, 60 to 120 days.

Confidential Page 19 of 50

- Country: Bangladesh, Kenya, Pakistan, Tanzania.
- Discharge destination: Home, Nutritional Rehabilitation Unit.
- All participants who received 100% of doses during treatment.
- Method of delivery: C-section, vaginal birth.
- Bilateral pedal edema at baseline: Yes, No.
- Prior Infant Antibiotic use: Yes, No.
- Concomitant Infant Antibiotic/Probiotic use through Day 56 visit: Yes, No.
- Proportion of feedings through Day 56 from breastmilk: 100%, 75 to 99%, 50 to 74%, 25 to 49%, < 25%.

Other subgroups may be considered in the final analysis. Summary statistics for subgroups will be reported for subgroups with greater than 5 participants in each of the treatment arms. Further details on subgroup analysis are provided in the relevant efficacy and safety sections below.

Confidential Page 20 of 50

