11.4.1 Dose storage

The following data will also be collected at each visit during the treatment phase (see Appendix 1) for study intervention storage information:

- where the study intervention is being stored (at the local health centre, the home of a participant in a refrigerator, the home of a participant in a cooler, or in a refrigerator at a neighbour's home). The final categories may be adapted to appropriately reflect the data collected.
- if refrigeration was off during storage (and how many doses were compromised).

Place of storage will be summarized using frequencies and percentages by treatment in a table for entire treatment period. A listing will be presented including place of storage, if refrigeration was off during storage, how long refrigeration was off, and number of doses compromised. This analysis will be presented for the Safety population.

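### The compliance score has no one-per-day cap, so a same-day replacement dose can offset a missed day and carry an infant over the 80% Per-Protocol limit; the dose-count bins also overlap at 28 and stop there.

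*SAP*

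**What the plan says.** SAP section 11.4 gives the score as 100 times doses administered over days on study intervention. The numerator "is the actual number of doses administered as per exposure eCRF". Four statements qualify it:

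- Repeats: "If a dose was re-administered due to vomiting within 30 minutes/spitting out the dose will be counted as one dose".
- Doses spilled with no part given are recorded as zero.
- Other second doses: "If a second dose was used and administered on the same day, it was recorded in a second record in the database".
- Deviations: "Deviations from planned dosing regimen will be used to consider if doses were used but not administered for any reason".

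The denominator is the number of days in the treatment period on which the infant could have been dosed. The same section sorts the number of doses into three bins: 28 (labelled as 100%), 14 to 28, and fewer than 14. It also reports how many infants reached a 100% score.

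The score is used in several places. In SAP section 8.1.5 a compliance deviation "is defined as compliance of less than 80" per cent. SAP section 8.2 lists a subgroup, "All participants who received 100% of doses during treatment", with no other definition. SAP section 11.5.2.3 correlates the score with change in WAZ. Section 11.5.2.4.2 lists it as a possible adjustment variable, and section 11.5.4.1 adjusts for it to take account of duration of dosing.

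Related data are collected but have no stated role in the score. Under protocol section 6.4, "whether the full dose was taken, and whether a repeat dose was administered will also be recorded in the diary" for Days 1 to 28. SAP section 11.4.1 records "if refrigeration was off during storage (and how many doses were compromised"), and this goes into a listing.

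**The concern.** The numerator counts doses and the denominator counts days. The ratio measures adherence only if a day can contribute at most one dose. The SAP secures this for the most foreseeable cause of a second dose, a repeat after vomiting or spitting out, but not for others. The clearest remaining case is a dose partly spilled and then replaced the same day: because some of the first dose was given, it is not set to zero, and the replacement is a second record.

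On the plain reading that day adds two, and the surplus cancels a day with no dose. At stake are who enters the Per-Protocol set, who counts as having had every dose, and the value of the covariate in the compliance-adjusted models. The dose-count bins have their own fault: they are neither mutually exclusive nor complete.

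**Working it through.** **Inputs.** One planned dose per day for 28 days (SAP section 7.1); Per-Protocol limit 80% (SAP section 8.1.5); bin edges from SAP section 11.4. Assumption: the infant stays on treatment for the whole course, so the denominator is 28.

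**1. The plan's own figure.** 28 doses over 28 days: 100 × 28/28 = 100%, matching the label on the 28-dose bin.

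**2. The limit in doses.** 0.80 × 28 = 22.4, so 23 doses are needed: 22/28 = 78.6% fails and 23/28 = 82.1% passes.

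**3. Effect of same-day second records.** Let d be the days with a dose and e the same-day second doses not due to vomiting or spitting out. The score as written is (d + e)/28; with a one-per-day cap it is d/28.

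| d | e | As written | Capped |
|---|---|---|---|
| 22 | 0 | 22/28 = 78.6%, fails | 78.6%, fails |
| 22 | 1 | 23/28 = 82.1%, passes | 78.6%, fails |
| 21 | 2 | 23/28 = 82.1%, passes | 21/28 = 75.0%, fails |
| 27 | 1 | 28/28 = 100% | 27/28 = 96.4% |
| 28 | 1 | 29/28 = 103.6% | 100% |

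The last two rows bear on the 100% group. An infant who missed a day reaches exactly 100%. One who missed none scores 103.6% and, if 100% is programmed as an equality, drops out.

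**4. Repeats after vomiting or spitting out.** These merge, so 28 dosing days with any number of such repeats still score 28/28 = 100%. There is no inflation here.

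**5. Bins.** A count of 28 satisfies both the first and the second bin. A count of 29, as in the last row, satisfies none.

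**6. Doses whose status is not stated.** The SAP gives no explicit rule for a partial dose, a vomited dose not repeated, or a storage-compromised dose that was given. Suppose 28 doses are recorded and k fall in these classes; the credit given is my assumption:

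- Full credit: 100% for any k.
- Half credit, k = 6: (28 − 3)/28 = 89.3%.
- No credit, k = 6: 22/28 = 78.6%, the first k that fails 80% (k = 5 gives 23/28 = 82.1%).

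The programmer's choice can therefore change Per-Protocol status. This shows that a rule is needed, not which rule is right.

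**The case against.** The sentence about a second record describes how data are stored; it does not say that both records enter the numerator. That is fair, but the numerator is defined as the administered count from the exposure form and the only merging rule is tied to vomiting or spitting out, so two programmers could derive different scores. The deviation clause does not settle it: it concerns doses used but not administered, whereas a replacement was administered.

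Per-Protocol membership does not rest on the score alone. The sponsor reviews important deviations individually before unblinding (SAP sections 8.1 and 8.1.5) and could exclude such an infant. This stands for the Per-Protocol set, but it does not correct the score entered in the correlation or the models.

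Three stronger readings are tempting, and the documents support none of them.

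- A reader might infer that the SAP counts partial, vomited-and-not-repeated and compromised doses as full dosing days. It is silent rather than explicit. Its compliance listing shows doses used, vomited and administered as separate items, and partial and vomited doses have their own table. Giving a partial dose no credit is also debatable, since the mITT and Safety definitions accept one as a dose received.
- A reader might infer from the 36 doses dispensed (9 per week × 4) that the score could reach 36/28 = 128.6%. That needs all eight spares to be given as same-day extras for reasons other than vomiting or spitting out. Repeats after vomiting, one stated purpose of the spares, are merged.
- A reader might infer that an infant whose weekly supply lost refrigeration has only 21/28 = 75% sound exposure yet stays in the Per-Protocol set. That assumes all seven doses were given anyway with none replaced. Spares cover compromised doses, families are told to contact staff about storage problems, and individual deviation review remains.

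**Conclusion.** The point holds as a defect in a stated rule, modest in reach. One extra record is enough to turn 78.6% into 82.1% and reverse a Per-Protocol exclusion, or to lift an infant with a missed day into the 100% group. This rests on a 28-day denominator and on reading the numerator literally. The overlap and gap in the bins need no assumption but affect a descriptive table only.

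The treatment of partial, unrepeated vomited and compromised doses is an omission to be filled, not an error in what is written. The primary and key secondary mITT models do not include compliance and are unaffected. What is affected is the Per-Protocol analyses, the 100%-of-doses subgroup, the correlation and the compliance-adjusted models. The documents give no frequency for any of these events, so the number of infants reclassified cannot be computed.

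**What to change.** 1. In SAP section 11.4, define the numerator as the number of days on which a dose was administered, at most one per day. Use this score for the 80% Per-Protocol rule, the 100%-of-doses subgroup, the correlation and the compliance-adjusted models.
2. Keep the raw dose count as a descriptive exposure table, with bins of 28 or more, 14 to 27, and fewer than 14.
3. Before unblinding, state how partial doses, vomited doses not repeated, and storage-compromised doses that were given count towards the score. What counts as an adequate dose is for the sponsor to decide. A supplementary score limited to days with a full, retained dose can be derived from the diary data.

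The cost is SAP wording and programming; the one-per-day score and the bins use data already collected. The documents do not say whether the compromised-dose count is linked to dosing days, so that part of item 3 may need a stated convention. The downside is that the Per-Protocol set may become slightly smaller.
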